2.1 Objectives

The Primary Objective of this study is:

- To evaluate the feasibility and acceptability of using a randomised crossover trial design to assess efficacy of CRT versus rate-responsive pacing in patients with HFpEF

The Secondary Objectives of this study are:

- To evaluate the use of diastolic and systolic reserve index as end-points in a trial design comparing CRT with RRP in patients with HFpEF
- To establish appropriate secondary end-points for future studies into the effect of CRT on:
 - i. Longitudinal and global longitudinal strain, torsion and untwisting, and diastolic dyssynchrony at rest and on exercise echocardiography,
 - ii. Exercise duration and oxygen carrying capacity measured by cardiopulmonary exercise (CPEX) testing,
 - iii. Distance walked in a 6-minute walk test,
 - iv. New York Heart Association (NYHA) functional class,
 - v. Quality of life using the Minnesota Living with Heart Failure Questionnaire (MLHFQ)
- To establish the likely drop-out rate following recruitment for the trial in terms of failed implantation and patient disengagement
- To establish the number of participants required to appropriately power a further randomised trial of CRT versus RRP in patients with HFpEF
- To identify possible confounders and covariates to inform sample size calculations for future studies

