After 12 weeks, the baseline parameters will be reassessed and patients will then have their device non-invasively reprogrammed to the remaining treatment allocation. (Visit length: approx. 4 hours)

Visit 4 – Assessments
After a further 12 weeks, the baseline assessments will be repeated. The pacemaker will be non-invasively reprogrammed to DDDR mode and the patient will go home. (Visit length: approx. 4 hours)

Optional extension (pending analysis of results)

Visit 5 – Reprogramming
If incremental benefit has been demonstrated with CRT above the benefit of RRP, the echocardiograms will be examined to establish the mechanism of improvement. Subjects will be invited to participate in a study extension using multisite technology. The device will be non-invasively reprogrammed to optimise the CRT settings targeted specifically for the mechanism identified. (Visit length: approx. 3 hour)

Visit 6 – Assessments
12 weeks after the final reprogramming, patients will attend for a final set of assessments as per baseline. Participant involvement will then cease. (Visit length: approx. 4 hours)

Total contact time with research team: Approximately 27 hours (22 hours without extension)

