3.2 Study Extension: Targeted Multipoint Pacing

Once all subjects have completed 12 weeks of RRP and 12 weeks of CRT (in either order), provisional analysis of the data will be performed. If an incremental benefit is shown for CRT above the benefit of RRP, analysis of echocardiograms before and after CRT will be performed to elucidate the mechanisms. Subjects will be invited to participate in a study extension. The pacemakers will then be non-invasively programmed using multisite optimisation to administer optimised CRT targeted to the specific mechanism of action. Final assessments will occur after 12 weeks, following which the participant involvement will end.

If no incremental benefit is shown for CRT at the initial analysis, the study will end at this point (after 24 weeks).

Incremental benefit for CRT will be defined as a statistically significant difference between average values for RRP and for CRT in paired t-tests in one or more of the following parameters: a) echocardiographic: diastolic reserve index; systolic reserve index; left ventricular end-systolic volume; left ventricular end-diastolic volume; tricuspid regurgitant peak velocity; torsion and untwisting on strain imaging; global longitudinal strain; b) cardiopulmonary exercise testing: peak oxygen consumption; exercise duration; VE-VCO₂ slope; c) distance walked on 6-minute walk test.

Ongoing pacemaker function will be a clinical decision based on patient preference and objective markers such as 6MWT. Long-term pacemaker follow-up will take place at [name] CRT clinic at University Hospital of Wales. All medications can be continued as prescribed for the duration of the study, but medication changes should be noted during follow-up.

4. Criteria for Evaluation

At each 12-week stage, the following will be assessed:

1. Change in end-diastolic volume
2. Change in end-systolic volume
3. Change in ejection fraction (Simpson's Biplane method)
4. Change in left ventricular filling by pulsed-wave Doppler of mitral inflow (peak E and A wave velocities, E wave deceleration time, A wave duration, diastolic filling time (DFT))
5. Change in pulmonary venous Ar (Atrial reversal) duration.
6. Change in left and right ventricular isovolumic relaxation time (IVRT) and isovolumic contraction time (IVCT)
7. Change in peak diastolic suction velocity (V_p)
8. Change in peak systolic twist (torsion) and in untwisting rate on speckle tracking

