9. Myocardial velocity imaging (MVI) in basal anterior, inferior, septal and lateral walls to assess:
 - a. Change in peak systolic velocity (s')
 - b. Change in peak early diastolic wave velocity (e')
 - c. Change in time from onset of QRS to onset of s' wave
 - d. Change in time from onset of QRS to peak e' wave
10. Change in duration of pulmonary venous a wave
11. Change in peak longitudinal strain in 12 wall segments, and peak global longitudinal strain (GLS) in 12-segment model
12. Change in pulmonary pressures as measured by tricuspid regurgitant jet peak velocity
13. Change in above parameters on exercise echocardiography where feasible due to image quality
14. Change in peak oxygen consumption (VO_2 max) and slope of ventilation to carbon dioxide production (VE- VCO_2 slope) on exercise
15. Change in exercise capacity as defined by duration of exertion and work-level achieved on cardiopulmonary exercise testing
16. Change in blood pressure response to exercise
17. Change in distance walked on 6-minute walk test
18. Change in New York Heart Association Functional Class
19. Change in Minnesota Living with Heart Failure Questionnaire score

5. Statistical Analysis Plan

Enrolled subjects will be analysed in a per protocol fashion. Estimates of period effects will be made by performing an unpaired t-test on the mean difference between the two treatment orders. Carryover effects will be estimated by performing a t-test comparing the mean within patient score (the mean of the two period means for each patient) with the mean between the treatment arms. If significant period or carry-over effects exist, then only the first period will be analysed.

The change in exercise, echocardiographic, functional class and wellbeing parameters will be evaluated using paired sample t-tests. A Wilcoxon signed rank test will be employed as a test of robustness.

The settings in the study extension will be compared with the CRT programming during the initial crossover period for each patient using paired sample t-tests (this may have taken place in period 1 or period 2).

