Where normality of distribution is not found, attempts will be made to transform the data using a suitable mathematical function. Where this is not possible, the Mann-Whitney U test will be employed. Analysis of categorical data will be by Chi-squared tests. Normality will be evaluated using visual assessment histograms and Q-Q plots. Significance will be tested at the 95% confidence level for all analyses, including calculation of period and carry-over effects.

An intention to treat analysis will be reported if the drop-out rate exceeds 10%. Corrections for multiplicity will not be made due to the exploratory nature of this data. No subgroup analysis is planned. Where data is missing, analysis will only be completed if 80% or more of data is present. For each analysis performed, subjects with data missing will be excluded from the individual parameter analysis, but will be included where data is present. Interim analysis will not be performed, except in the event of study discontinuation. Study discontinuation will occur only in the event of safety concerns, as detailed below, or in the event of failure to recruit within the planned timeframe.

Drop-out rates and reasons will be recorded at each stage. This will be presented as a CONSORT diagram in the publication of study results.

All statistical analysis will be double-checked by a statistician prior to dissemination of study results.

6. Study Administration

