Appendix: Exercise Echocardiography Protocol

Exercise:

- Workload at anaerobic threshold will be calculated using results from the introductory cardiopulmonary exercise test.
- For echocardiography, a ramped stress protocol, aiming to achieve image acquisition at baseline, and at 50% and 100% of anaerobic threshold (AT, also known as ventilatory threshold) will be used.
- A pedalling rate of 55–65 r.p.m. will be aimed for.
- Ramp to 50% of AT workload will occur over one minute, with a further minute for stabilisation of heart rate and vasculature.
- Images will then be obtained over the following three minutes.
- Once images have been obtained, a further ramp will occur to AT workload over one minute with a further minute for stabilisation.
- Images will be obtained at AT over three minutes.
- Following image acquisition, the test will cease.
- Should the subject be unable to maintain pedalling rate or exercise at AT, the workload will be reduced by 25% to enable continued scanning until image acquisition is complete.
- Total exercise time for this test will be 10 minutes.
- Workload at each stage will be kept the same for each test that a participant performs.

Study Diagram

* Pacemaker settings at end of study to be determined clinically based on patient preference and objective measures such as 6MWT

Schedule of Evaluations

Visit	Screening	Visit 1	Visit 2	Visit 3	Visit 4 ^c	Provisional Analysis: once data obtained from all subjects	Visit 5	Visit 6 ^c
Day/Week/Month	≤ -12 Weeks ^a	Day 0	Day 1 +/- 7 days	Week 12 ^b	Week 24 ^b		+0 weeks	+ 12 weeks
Informed consent	X							
Demographic data	X							
Medical history	X							
Medical examination	X	X		X	X			X
Medication history	X	X		X	X			X
Height & weight		X						
Inclusion and exclusion criteria	X	X						
12-lead ECG	X	X		X	X			X
NYHA Functional Assessment	X	X		X	X			X
6-minute walk test		X		X	X			X
MLHFQ		X		X	X			X
Echocardiogram		X		X	X			X
Cardiopulmonary exercise test		X		X	X			X
Implant CRT device			X					
Randomisation ^a			X					
Reprogram device				X	X		X	

Abbreviations: CRT = cardiac resynchronisation therapy, NYHA = New York Heart Association, MLHFQ = Minnesota Living with Heart Failure Questionnaire, ECG = Electrocardiogram

a Randomisation must occur within 12 weeks of screening visit; <https://www.randomizer.org/>

b ±7 days permissible for follow-up visit

c Study termination occurs after Visit 4 if no incremental benefit for CRT seen and after Visit 6 if benefit seen

References

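### Section 3.2 defines incremental benefit of CRT as any significant difference, so a significant worsening on CRT would also meet it, and the echo measurement stage is left open

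*Combined protocol and SAP*

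**What the plan says.** Section 3.2 (Study Extension) holds the only operative definition. Incremental benefit is "a statistically significant difference between average values for RRP and for CRT in paired t-tests in one or more of the following parameters". The list that follows has eight echocardiographic quantities: the two reserve indices, the two left ventricular volumes, tricuspid velocity, torsion, untwisting and global longitudinal strain. It adds three cardiopulmonary exercise measures and the walk distance. If the rule is met, the extension is offered. If not, the study ends at 24 weeks. Note c to the Schedule of Evaluations repeats this.

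The intent appears in Section 2.4, Visit 5: "If incremental benefit has been demonstrated with CRT above the benefit of RRP, the echocardiograms will be examined to establish the mechanism of improvement".

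Section 5 sets the threshold, "Significance will be tested at the 95% confidence level for all analyses", and adds: "Corrections for multiplicity will not be made due to the exploratory nature of this data".

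On measurement stage, Section 2.1 speaks of "torsion and untwisting, and diastolic dyssynchrony at rest and on exercise echocardiography". Section 4, item 13, adds "Change in above parameters on exercise echocardiography where feasible due to image quality". The Appendix describes a ramped protocol "aiming to achieve image acquisition at baseline, and at 50% and 100% of anaerobic threshold". Section 2.3 gives the reserve-index formulae without saying which exercise stage supplies the change from rest. Section 3 states that patients are blinded to allocation and investigators are not.

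**The concern.** The term being defined is a benefit, but its definition requires only a difference. Applied literally, a significant fall in peak oxygen consumption on CRT would keep the study open and start a search for the mechanism of an improvement that had not occurred.

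The missing sign cannot always be supplied from elsewhere in the documents. Section 1.1 treats a fall in end-systolic volume as response to CRT, but no section gives a favourable direction for end-diastolic volume, which is also on the list. Tricuspid velocity and the VE-VCO2 slope likewise have no stated sign.

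The stage is a second gap. The same echo parameter may be available at rest and at two exercise workloads, and Section 3.2 does not say which one counts. The rule is applied by people who know the allocation, so a direction or stage not fixed beforehand could be settled once the results are visible.

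**Working it through.** The documents give no chance-pass rate for this rule, so there is no stated figure to reproduce.

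**Inputs from the documents**
- Tests: 12 (8 echo, 3 exercise-test, 1 walk-test), or 11 if torsion and untwisting count as one (Section 3.2).
- Pass rule: at least one significant paired t-test (Section 3.2).
- Level: 5% per test, uncorrected (Section 5).
- Patients: 10 (Section 2.2.2). The 80% completeness rule in Section 5 allows as few as 8 pairs.

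**Assumptions**
- Tests are two-sided. Section 5 gives only the confidence level.
- There is no true treatment effect.
- Paired differences share a common correlation after each parameter is oriented so that positive favours CRT. The documents give no correlations, so a range of 0 to 0.9 is shown.
- The first-period-only fallback in Section 5 is not modelled.

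**Independent tests, exact, 12 parameters**
- Any significant difference: 1 − 0.95^12 = 0.460.
- At least one favourable difference: 1 − 0.975^12 = 0.262.
- Unfavourable differences only: 0.460 − 0.262 = 0.198.
- With 11 parameters, the first two become 0.431 and 0.243.

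**Correlated tests, simulated** (100,000 null trials, 10 patients, 12 parameters; the row for correlation 0 is exact)

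| Assumed correlation | Rule as written | Of which unfavourable only | Favourable direction required |
|---|---|---|---|
| 0 | 46.0% | 19.8% | 26.2% |
| 0.3 | 40.9% | 19.7% | 21.2% |
| 0.5 | 33.9% | 16.8% | 17.1% |
| 0.7 | 25.5% | 12.8% | 12.7% |
| 0.9 | 14.8% | 7.4% | 7.3% |

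With 8 patients the rule as written gives 46.2%, 34.4% and 15.1% at correlations 0, 0.5 and 0.9, which is nearly the same. The unfavourable-only share of chance passes is 0.198/0.460 = 43% at correlation 0, and about half at 0.5 (16.8/33.9) and at 0.9 (7.4/14.8).

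**Which parameters the stage gap touches**
- Four are fixed by the test itself: the three exercise-test measures and the walk distance.
- Two reserve indices already combine rest and exercise. Only the exercise stage is open.
- Six are fully open: end-systolic volume, end-diastolic volume, tricuspid velocity, torsion, untwisting and global longitudinal strain.

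The number of tests therefore depends on the reading. One stage each gives 12. Rest plus one exercise stage for the six gives 12 + 6 = 18. Every stage in the Appendix gives 6 × 3 + 2 × 2 + 4 = 26.

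| Tests | As written, correlation 0 / 0.5 / 0.9 | Favourable required, correlation 0 / 0.5 / 0.9 |
|---|---|---|
| 12 | 46.0 / 33.9 / 14.8% | 26.2 / 17.1 / 7.3% |
| 18 | 60.3 / 42.9 / 16.7% | 36.6 / 21.8 / 8.3% |
| 26 | 73.6 / 51.4 / 18.3% | 48.2 / 26.4 / 9.1% |

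**The case against.** The best defence is that the direction is obvious. The defined term is a benefit of CRT over rate-responsive pacing, and Section 2.4 refers to improvement. The background also orients several parameters: reserve indices, torsion, untwisting and strain are described as reduced or impaired in HFpEF, a lower end-systolic volume is response, and higher oxygen consumption is improvement. This stands as evidence of intent. A reader might infer from the literal wording that the team would open the extension on evidence of harm, and the documents do not support that. Intent still does not complete the rule, and for end-diastolic volume there is no stated direction to fall back on.

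On stage, Section 4 names the volumes, twist, strain and tricuspid velocity first and lists exercise values separately in item 13. That favours a resting reading and 12 tests. It is not conclusive, since Section 2.1 covers both conditions. The 26-test count is the extreme case, and nothing says that every stage counts.

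Three stronger readings should be resisted:
- That the absence of multiplicity correction is an error. Section 5 discloses it and gives a fair reason for an exploratory study. Stating a chance-pass rate would be presentational.
- That mixed results are unhandled. Asking for one or more parameters settles this: one qualifying parameter suffices whatever the others show.
- That no parameter has a defined stage. The exercise-test and walk-test measures do.

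**Conclusion.** The point holds as a defect in the wording of a decision rule. Read literally, Section 3.2 accepts a significant worsening on CRT as incremental benefit, against the plan's own stated aim. Under the null and the assumptions above, unfavourable-only passes make up roughly 7 to 20 percentage points of a literal chance-pass rate of 15% to 46%. Adding direction brings that rate to 7% to 26%. The ranges rest on assumed correlations, two-sided testing and 12 tests.

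The open stage for six echo parameters, and the open exercise stage for the two reserve indices, is a real but smaller gap. It matters mainly because the investigators are unblinded. The list, the test and the threshold are all prespecified, so it would be too strong to say that the outcome of the rule is generally open to choice after the data are seen.

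Severity is minor to moderate. The trigger is exploratory, the extension is optional and non-invasive, and neither the primary feasibility objective nor long-term pacing decisions depend on it.

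**What to change.** In Section 3.2, reword the definition to require *a statistically significant paired difference in favour of CRT* in one or more of the listed parameters. Add a short table, fixed before any outcome data are examined, that gives:
- the favourable direction for each parameter, including end-diastolic volume;
- one measurement stage for each of the six echo parameters open to more than one (rest, 50% or 100% of anaerobic threshold);
- the exercise stage that supplies the change in each reserve index.

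The cost is one reworded sentence and one table, with no extra patients, visits or measurements. No multiplicity correction, mixed-result rule or disclosure of a chance-pass rate is needed.

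### A significant period or carry-over test discards period 2, although a period effect can be adjusted for, and the extension criterion is not reconciled with this rule

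*Combined protocol and SAP*

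**What the plan says.** Section 5 (Statistical Analysis Plan) tests for a period effect with an unpaired t-test between the two orders. It tests for carry-over with a t-test on each patient's average, described as "the mean of the two period means for each patient". It then states: "If significant period or carry-over effects exist, then only the first period will be analysed". The level is the same throughout: "Significance will be tested at the 95% confidence level for all analyses, including calculation of period and carry-over effects".

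The main comparison has no period term: "The change in exercise, echocardiographic, functional class and wellbeing parameters will be evaluated using paired sample t-tests". A Wilcoxon signed rank test is the robustness check. No period-adjusted analysis appears in the document.

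Section 3.2 governs the extension. Once every patient has completed both modes, "provisional analysis of the data will be performed". The criterion reads: "Incremental benefit for CRT will be defined as a statistically significant difference between average values for RRP and for CRT in paired t-tests", in at least one of a list of echocardiographic, exercise and walk-test parameters. Section 5 adds: "Corrections for multiplicity will not be made due to the exploratory nature of this data".

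The results are meant to feed later work. Section 2.2.2 says 10 patients will allow the treatment difference to be estimated, and one objective in section 2.1 is "To establish the number of participants required to appropriately power a further randomised trial of CRT versus RRP in patients with HFpEF".

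**The concern.** There are four parts, the first being the main one.

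1. A period effect common to both orders cancels when the period 1 minus period 2 differences are compared between orders. It does not justify dropping period 2.
2. The carry-over test uses data from both periods. If it and the period 1 fallback are on the same scale (both raw, or both change from baseline), they are correlated, and choosing the analysis by the pre-test raises the type I error. Section 5 does not state the scale.
3. If neither pre-test is significant, the paired t-test leaves the period effect in the error. If the orders are unequal in size, part of it also enters the treatment estimate.
4. A paired t-test cannot be run on period 1 alone. Section 3.2 does not say whether the section 5 fallback applies to the extension criterion. Section 5 itself compares the extension with CRT data from either period and makes no exception for a discarded period 2.

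At stake are the precision of the treatment estimate carried into a future trial and the decision to open the extension.

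**Working it through.** **Inputs from the documents.** 10 patients (2.2.2); 1:1 randomisation to the two orders (section 3); 5% level for treatment tests and pre-tests (section 5). The plan gives no power, effect size or SD, so it has no figure to reproduce.

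**Assumptions.** Two-sided tests; 5:5 split; outcome SD 1; within-patient correlation r of 0.5 to 0.9, also with baseline. Period effects are in SDs of the within-patient difference.

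**How often the rule fires by chance.** With two independent 5% tests: 1 − 0.95² = 9.75% per parameter. About half of this comes from the period test alone.

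**Precision when it fires.**
- Period 1, raw: SE = √(2/5) = 0.632.
- Period 1, change from baseline: SE = √(2(1−r) × 2/5).
- Both periods, period-adjusted: SE = √(2(1−r)/10).
- 95% CI half-width = 2.306 × SE (8 df).

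| r | Raw SE (half-width) | Change SE (half-width) | Adjusted SE (half-width) | Raw / adjusted | Change / adjusted |
|---|---|---|---|---|---|
| 0.5 | 0.632 (1.46) | 0.632 (1.46) | 0.316 (0.73) | 2.0 | 2.0 |
| 0.7 | 0.632 (1.46) | 0.490 (1.13) | 0.245 (0.56) | 2.6 | 2.0 |
| 0.9 | 0.632 (1.46) | 0.283 (0.65) | 0.141 (0.33) | 4.5 | 2.0 |

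This loss does not depend on any assumed period effect.

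**Power, by simulation.** The treatment effect is 0.996 SD of the difference, which gives the paired test 80% power at n = 10 (noncentrality 3.150; 3.150/√10 = 0.996). The ranges cover r and all four combinations of raw or change scale for the carry-over test and the fallback.

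| Period effect | Rule fires | Power, current rule | Paired test, no rule | Period-adjusted |
|---|---|---|---|---|
| 0 | 10% | 73%–76% | 80% | 79% |
| 0.5 SD | 32% | 53%–61% | 72% | 79% |
| 1 SD | 80% | 19%–36% | 48% | 79% |

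The period test alone accounts for 5, 27 and 75 points of the firing rates. Discarding period 2 costs more than omitting the period term.

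**Type I error of the two-stage rule, no period effect.** About 7.0% to 8.5% when both steps use raw values, 7.1% when both use change from baseline, and 5.1% to 5.2% when only the fallback uses change.

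**Unequal orders.** With n₁ and n₂ patients per order, the paired estimate is shifted by (n₁ − n₂)/10 times the period effect: 0.2 times at 6:4 and 0.4 times at 7:3. With a 0.5 SD period effect, the whole rule has type I error 4.6% to 7.1% (6:4) and 6.4% to 8.8% (7:3). The adjusted test stays at 5%.

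**Extension criterion.** Counting torsion and untwisting separately, section 3.2 lists 12 parameters. The simulation (20,000 trials, not replicated) assumed no true effects, between-parameter correlation 0 to 0.7, and the rule applied parameter by parameter, which the plan does not state.
- The literal paired criterion and the criterion with fallback disagree in 12% to 22% of trials (raw fallback) or 4% to 6% (change fallback). With a 0.5 SD period effect the figures are 16% to 31% and 11% to 18%.
- The criterion is met by chance in 25% to 46% of trials (literal paired), 36% to 65% (raw fallback), 27% to 47% (change fallback) or 26% to 46% (adjusted). For independent parameters, 1 − 0.95¹² = 46%.

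**The case against.** **Weight.** This is a 10-patient exploratory study whose primary objective is feasibility. It claims no power. With no period effect the rule costs only 3 to 6 points of power against adjustment (79% less 73% to 76%). The large losses need period effects of 0.5 to 1 SD, which several features work against: clinical stability (2.5), the familiarisation test (2.11) and fixed workloads (Appendix). This stands, and it is why the consequence is modest. A period effect is still not implausible: period 1 begins in the pacing laboratory straight after implantation, and medication may change during follow-up.

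**Type I error depends on the reading.** Section 4 lists most outcomes as changes, while the carry-over test refers to a patient score. If only the fallback uses change from baseline, there is no material inflation. This stands; the remaining fault is that the scale is unstated. The unequal-order figures also mix this inflation with the missing period term. At a 0.5 SD period effect, the paired test alone rejects 3.8% at 6:4 and 6.0% at 7:3.

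**Section 3.2 can be read literally.** The paired criterion can then always be computed. That makes it a point to reconcile rather than a flat contradiction.

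**The rule protects against carry-over.** There is no washout, and section 2.5 says ventricular volumes change slowly; both volumes are extension parameters. With no treatment effect and carry-over of 1 SD of the difference, the adjusted test falsely rejects in 29% of trials, against 17% to 20% under the rule. This is a real trade-off, but the protection is mostly accidental. The carry-over test detects such an effect only 6% to 13% of the time, and the gain comes mainly from carry-over tripping the period test (29%). At 0.5 SD the figures are 11% against 9% to 12%, and at 0.25 SD 6.4% against 6.2% to 9.5%.

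**Conclusion.** The concern holds and should be fixed. Dropping period 2 because of a period effect is unnecessary under any assumption about scale or correlation. The roughly 10% chance of firing with no true effects follows from the plan's own 5% levels. When the rule fires, the standard error is at least doubled for correlations of 0.5 or more. The power figures are scenarios built on assumed correlations, period effects and a treatment effect, not properties of this trial. Type I inflation applies only on some readings of the scale. The extension criterion and the fallback rule need reconciling whatever the simulations show. The harm is limited to the treatment estimate for a future trial and to the extension decision; the feasibility objective is unaffected.

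**What to change.** - Delete the first-period-only rule from section 5.
- For every continuous parameter, use one prespecified period-adjusted analysis of both periods, whatever the period and carry-over tests show. This is an unpaired t-test of the period 1 minus period 2 differences between the two orders, or the equivalent mixed model (sequence, period and treatment fixed, patient random). Use a rank-sum test on the same differences as the robustness check.
- Name this analysis in section 3.2 in place of the paired t-tests.
- Report period and carry-over estimates with 95% confidence intervals that trigger nothing.
- Show period 1 estimates as descriptive sensitivity results, stating whether they are raw or change from baseline. State that true carry-over would still bias the main estimate.

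**Cost.** Some rewording, one line of code and one degree of freedom (8 instead of 9), taking power from 80% to about 79% with no period effect. Randomisation need not change, because the adjusted test holds 5% at 6:4 and 7:3. The chance of opening the extension by luck stays at about the level the plan already accepts.

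**What it does not solve.** Carry-over of half the treatment effect reduces the adjusted estimate to 75% of the truth (power 55%, against 50% to 53% under the current rule). Carry-over equal to the effect reduces it to 50% (power 28%, against 22% to 31%).
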